6.1.2 Handling of Dropouts and Missing Data

For the primary efficacy analysis of all four co-primary efficacy endpoints, and all secondary efficacy analyses of change from Baseline to Week 12 in symptoms and signs of vulvovaginal atrophy and the global symptom score, missing data will be imputed using the last observation carried forward (LOCF) methodology. Only post-Baseline values will be carried forward.

As sensitivity analyses, the four co-primary efficacy variables will also be analyzed on an as observed case basis with no imputation of missing data, in order to assess the robustness of the results.

All other analyses will be conducted on an as observed case basis, that is, no further imputation of missing data will be carried out unless expressly stated otherwise.

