3.1 Study Design

This study is a double-blind, randomized, dose-ranging, placebo-controlled multicenter study with four parallel groups. Approximately 25 sites in Europe will be included in the study. The study setting will include academic hospitals and gynecological clinics. The study population is postmenopausal women who report moderate to severe vaginal dryness as their most bothersome symptom in addition to other symptoms and/or signs of postmenopausal vulvovaginal atrophy.

After providing informed consent, potential subjects will be evaluated during the screening period to determine if they are eligible to participate in the study. A screening identification number will be assigned to each eligible subject according to their order of arrival into the study at screening visit. Subjects who meet all of the inclusion criteria (see Section 4.1.1) and none of the exclusion criteria (see Section 4.1.2) will be randomized into the study. A total of 280 subjects will be enrolled and randomly allocated to one of the four treatment groups (0.005%, 0.002%, or 0.0008% estriol vaginal gel or placebo vaginal gel); the allocation to treatment group will be 1:1:1:1. A blocked randomization across the entire study (i.e. all sites as a whole) will be used. Subjects will be assigned a randomization code according to their order of arrival into the study at the Baseline Visit. Initial treatment consists of daily vaginal administration of 1 gram of randomly-assigned estriol gel or placebo gel using the supplied applicator. After 21 days of daily administration, treatment will continue with twice-weekly administration up to Week 12 (i.e., Mondays and Thursdays).

The duration of trial participation for each woman is expected to be approximately 20 weeks (from Screening to End-of-Study phone call) although the time on study drug will be approximately 12 weeks. Subject completion is defined as the completion of all phases of the study, including the End-of-Study phone call to be performed for safety purposes at Week 16.

An overview of the study visit procedures is given in the Schedule of Events (Table 1). Details of specific procedures and testing are provided in Section 6.

Table 1: Schedule of Events

Procedure	Screening Visit	Baseline	Week 3	Week 8	Week 12/ Early Termination	Week 16/ End of Study Phone Call
Visit Window (days)	-30 to -1	1	21 ±3	56 ± 5	84 ± 5	112 ± 5
Informed consent	X					
Randomization		X				

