4.2.2 Handling of Withdrawals

Subjects are free to withdraw from the study or study drug at any time upon request. Subject participation in the study may be stopped at any time at the discretion of the investigator or at the request of the Sponsor.

Subjects who discontinue study drug or active participation in the study will no longer receive study drug. When a subject withdraws from the study, the reason(s) for withdrawal shall be recorded by the investigator on the relevant page of the electronic case report form (eCRF).

Any subject who prematurely terminates participation and who has received at least one dose of the test or reference product will undergo a final examination (see Section 6.1.5 for details).

If study participation is terminated due to an AE possibly related to the study drug or study examinations, the subject must be followed-up by additional examinations according to the medical judgment of the investigator until the abnormal condition is resolved or the investigator deems further observations or examinations to be no longer medically indicated. Subjects who fail to return for final assessments will be contacted by the site (via two telephone calls and then a registered letter) in an attempt to have them comply with the protocol.

It is vital to obtain follow-up data on any subject withdrawn because of an AE or serious AE (SAE). In every case, efforts must be made to undertake protocol-specified, safety, follow-up procedures. All subjects withdrawn from the study should be registered accordingly on the Interactive Web Response System (IWRS).

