6.1.3 Week 3 Visit

This visit will be scheduled on the day after having completed 21 days of treatment. For organizational reasons, a deviation of 3 days before or after the scheduled date is allowed, with the investigator attempting to schedule the visit as close as possible to the estimated ideal date.

The following procedures will be performed:

- Evaluation of symptoms and signs of vaginal atrophy, including vaginal dryness.
- Determination of vaginal pH
- Vaginal smear for evaluation of vaginal cytology
- Recording of adverse events
- Recording of concomitant medications

- Reconciliation of returned medication
- Dispensing adequate medication supplies via IWRS through the Week 8 Visit (two medication kits)

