6.2.2 Vaginal pH Determination

For pH determination, a reactive pH strip will be used. On each occasion, the investigator will insert the strip into the vagina and moisten it as much as possible with the vaginal wall

secretions. Once adequate wetting has been achieved, the colors on the strip will be checked against a standard pH scale (provided by the manufacturer) to determine the pH value. The reading should be made while the strip is still moist. The strips will be discarded appropriately once the pH has been recorded.

Vaginal pH determination will be performed at Screening Visit, at the Week 3 Visit, and at the Week 12/Early Termination Visit.

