6.3.1.1 Change from Baseline to Week 12 in Severity of Vaginal Dryness

Vaginal dryness is one of the five symptoms of vulvovaginal atrophy, and is self-assessed by the subject at the Screening, Week 3 and Week 12 / Early Termination visits.

Each symptom will be scored by the subject using a numeric scale from 0 to 3, as follows:

0	Absent:	The symptom is not present
1	Mild:	The symptom is of mild intensity
2	Moderate:	The symptom is of moderate intensity
3	Severe:	The symptom is severe in intensity

The number and percentage of subjects with each severity of vaginal dryness at each visit will be summarized by treatment in a general summary table of symptoms of vulvovaginal atrophy.

Given that the Inclusion Criteria for the study require the subject to have moderate (score of 2) or severe (score of 3) vaginal dryness at Baseline (Screening), the change from Baseline to Week 12 may take the possible values ranging from -3 (Severe at Screening; Absent at Week 12) to 1 (Moderate at Screening; Severe at Week 12).

The number and percentage of subjects with each ordinal change from Baseline to Week 12 value (-3, -2, -1, 0 and 1) will be summarized by treatment group.

The change from Baseline to Week 12 in vaginal dryness will be analyzed using a Wilcoxon Rank Sum test, controlled for country, to obtain the one-sided p-values for each treatment

comparison (0.005% Estriol versus placebo, 0.002% Estriol versus placebo and 0.0008% Estriol versus placebo) by means of the FREQ procedure in SAS with the SCORES = RANK option. The Hodges-Lehmann estimate of median difference between treatment groups will also be presented for each of the three treatment comparisons above, along with 95% CIs, by means of the NPAR1WAY procedure in SAS. Hodges-Lehmann estimates will be presented without the adjustment for country, since SAS does not currently produce Hodges-Lehmann estimates when covariates are included. Missing values at Week 12 will be estimated using LOCF methodology for the ITT population analysis only. Only post-Baseline values will be carried forward.

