6.3.1.2 Change from Baseline to Week 12 in Severity of Vaginal pH

A vaginal pH determination will be performed at the Screening, Week 3 and Week 12 / Early Termination visits.

The vaginal pH will be summarized using descriptive statistics for continuous variables by treatment and visit. The change from Baseline (Screening) value will also be summarized for all post-Baseline visits.

The mean change in vaginal pH from Baseline to the Week 12 / Early Termination visit will be analyzed using a parametric analysis of covariance (ANCOVA) model. The model will include treatment and country as fixed effects and the Baseline (Screening) pH will be used as a covariate. The adjusted (least-square) mean (LS Mean) change in vaginal pH from Baseline to Week 12 will be presented for each treatment, along with the corresponding SE. The difference in LS Means between treatment groups (0.005% Estriol versus Placebo, 0.002% Estriol versus Placebo and 0.0008% Estriol versus Placebo) will also be presented with 95% CI and one-sided p-value. The p-values for the model parameters of country and Baseline pH will also be presented. Model assumptions will be examined and, if required, a Wilcoxon Rank Sum test as described for vaginal dryness (Section 6.3.1.1) will be used. Missing values at Week 12 will be estimated using LOCF methodology for the ITT population analysis only. Only post-Baseline values will be carried forward.

6.3.1.3 Change from Baseline to Week 12 in Proportion of Superficial Cells of the Vaginal Epithelium

Vaginal smears will be performed at the Screening, Week 3 and Week 12 / Early Termination visits. Two vaginal smears will be collected per subject at each visit, with one cytological sample sent to the central laboratory [REDACTED] for analysis, and one sample retained at site for backup purposes. The samples sent to [REDACTED] will be evaluated by two different cytopathologists who will be blinded to subject, treatment assignment and to each other's evaluations. The number and percentage of superficial cells will be provided for each pathologist's cytologic evaluation, and the percentages will be converted to proportions for statistical presentation.

The proportion of superficial cells of a given subject and visit to be used for analysis will be derived as the mean result across the two pathologists. The evaluations of both pathologists must be verified by the Clinical Research Associate (CRA) in order to be considered for final analysis.

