6.3.1.6 Sensitivity Analysis

Observed Case Analysis

The robustness of the LOCF approach for missing data will be addressed by completing a sensitivity analysis. This will be an observed case analysis of the endpoints described in Sections 6.3.1.1 to 6.3.1.5, with no imputation methods for missing data, in order to assess the robustness of the primary efficacy results.

Mixed Model for Repeated Measures Analysis

As additional sensitivity analyses, the endpoints described in **Sections 6.3.1.1 to 6.3.1.5** will each be analyzed using a mixed effects model for repeated measures (MMRM) on the ITT population. The models will include treatment, visit, treatment-by-visit interaction, country and Baseline value as fixed effects, and will use an unstructured (general) residual covariance matrix for repeated records within subjects. For each endpoint, the LS mean change in the endpoint from Baseline will be presented for each treatment by visit and overall, along with the corresponding SE. The difference in LS means (0.005% Estriol versus Placebo, 0.002% Estriol versus Placebo and 0.0008% Estriol versus Placebo) will also be presented with 95% CI and one-sided p-value for each visit and overall. The p-values will also be presented for the model parameters of visit, treatment-by-visit interaction, country and Baseline value.

Only ITT population subjects with both a Baseline and at least one post-Baseline measurement for a given endpoint will be included in the MMRM for that endpoint.

Due to the categorical nature of the vaginal dryness endpoint, the change from Baseline (Screening) vaginal dryness values and the Baseline (Screening) vaginal dryness values will be assigned ranks according to their order within each treatment group, and the MMRM will be conducted on the ranked values.

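### Primary LOCF can put a Week 3 value from the daily-dosing phase into the Week 12 contrast, which follows nine weeks of twice-weekly dosing

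*SAP*

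**What the plan says.** Protocol 7.8.1 and SAP 6.1.2 and 6.3.1 make LOCF on the ITT population the primary handling of missing Week 12 data for dryness, pH, superficial cells and parabasal cells. SAP 6.1.2 adds: "Only post-Baseline values will be carried forward".

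The values that could be carried are few:

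- **Dryness** (SAP 6.3.1.1) is "self-assessed by the subject at the Screening, Week 3 and Week 12 / Early Termination visits".
- **pH** (Protocol 6.2.2): "Vaginal pH determination will be performed at Screening Visit, at the Week 3 Visit, and at the Week 12/Early Termination Visit".
- **Cytology** (SAP 6.3.1.3): "Vaginal smears will be performed at the Screening, Week 3 and Week 12 / Early Termination visits".

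The Week 8 visit lists in Protocol 6.1.4 and SAP 4.1.4 contain no efficacy measure, and Protocol Table 1 agrees.

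On dosing, Protocol 3.1 says: "After 21 days of daily administration, treatment will continue with twice-weekly administration up to Week 12". On the timing of Week 3, Protocol 6.1.3 says: "This visit will be scheduled on the day after having completed 21 days of treatment", with a window of 3 days either way.

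Protocol 4.2.2 plans a final examination for every dosed woman who stops early. Protocol 6.1.5 and SAP 4.1.5 include dryness, pH and a smear in that visit.

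SAP 6.3.1.6 plans two sensitivity analyses: observed cases, and an MMRM with treatment-by-visit interaction on the ITT population. SAP 7.2.2 lists a gatekeeping table for each.

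**The concern.** LOCF is valid here only if the carried value has the same expected drug-placebo difference as the missing Week 12 value. The design gives a specific reason to doubt that. Week 3 closes a phase of seven applications a week, whereas Week 12 closes nine weeks at two a week. A woman whose last measurement is Week 3 enters the Week 12 analysis with a response to a regimen 3.5 times as frequent (7/2).

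The Week 12 contrasts feed the gatekeeping sequence, and Protocol 6.2 and SAP 6.3.1 define the minimal effective dose as the lowest dose that is significant against placebo. A carried effect from the daily phase could help a dose pass whose effect is not maintained. It could also count against a dose whose effect is still building.

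**Working it through.** **The plan's own figures.** They reproduce. For pH (difference -0.89, SD 1.33, one-sided 0.025), 48 per group gives 90.05% power. For dryness, 57 per group with the Table 2 proportions gives 90.6%. Inflation for dropout is 57/(1 - 0.18) = 69.5, hence 70 per group.

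**Inputs from the documents.** 70 per group; 18% dropout; pH SD 1.33; planning difference -0.89 (Protocol 7.5, SAP 6.1.4).

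**Assumptions.** The documents give neither a Week 3 effect nor the share of dropouts whose last value is Week 3. I borrow -0.89 as a Week 3 effect for illustration only. I let 25%, 50% or 100% of the 18% be carried from Week 3, equally in both arms.

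**Case A: Week 3 effect of -0.89, no effect at Week 12.** With f the share of each arm carried from Week 3:

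- False LOCF difference = -0.89 × f.
- Standard error = 1.33 × √(2/70) = 0.225.
- Error = chance that a t test with 138 degrees of freedom gives one-sided p ≤ 0.025 under that shift.

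| Dropouts carried from Week 3 | f | Women per arm | False pH difference | One-sided error, pH |
|---|---|---|---|---|
| 25% | 0.045 | 3.2 | -0.04 | 3.7% |
| 50% | 0.09 | 6.3 | -0.08 | 5.4% |
| 100% | 0.18 | 12.6 | -0.16 | 10.5% |

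The last figure is 10.6% by normal approximation. The same exercise for dryness lets carried active-arm women follow the estriol column of Table 2 and all others the placebo column. It gives about 3.7%, 5.1% and 9.3%. These are single-endpoint errors.

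I simulated Case A in large samples, with an assumed within-woman correlation of 0.3 or 0.6 and dropout unrelated to outcome. The likelihood-based Week 12 estimate, which is what the MMRM targets, was about 0 throughout. LOCF showed the false differences above, within simulation error.

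**The direction can reverse.** Suppose the true Week 12 difference is -0.89 for everyone and f = 0.18. LOCF is expected to show -0.89 × (0.82 + 0.18k), where k is the Week 3 effect divided by the Week 12 effect. With k = 0.75 this is -0.85; with k = 1.5 it is -0.97.

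**Case B: the effect is equal at both visits, but dropouts lose it.** Suppose women who stop have no drug effect at Week 12 and f = 0.18. The true average is -0.89 × 0.82 = -0.73. In simulation LOCF and the likelihood-based estimate both gave about -0.89. The MMRM does not cure this case; only an analysis that lets dropouts follow placebo addresses it.

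**The case against.** **Early Termination limits how many values come from Week 3.** This stands. A woman who attends that visit contributes its value, and a woman who leaves before Week 3 has no Week 3 value to carry. The 18% row is therefore a ceiling. Some carrying remains possible: Protocol 4.2.2 itself provides for women who fail to return, and a completer can lack a Week 12 smear. An Early Termination value before Day 21 also reflects daily dosing. The SAP analyses Week 12 and Early Termination together, with no rule on how long after the last dose such a value may count.

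**Sensitivity analyses already exist.** For pH and cytology the MMRM is specified down to its tables, so the dispute is largely about which analysis is primary. But SAP 6.8 describes it as exploratory, and no rule says what follows if it disagrees with LOCF. The dryness MMRM is a weaker check: its ranks are assigned inside each treatment group, which removes the difference between groups.

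**Stronger readings do not hold.** A reader might infer that LOCF overstates the effect, for instance by 5 to 22% for pH. That range needs a Week 3 effect of -0.89, 10 to 18% of women carried from Week 3, and a loss of half or all of the effect in those women. The documents give none of these, and -0.89 is a planning value for the Week 12 endpoint. A reader might also infer that the MMRM restores randomized women with no post-Baseline value. It does not: SAP 6.3.1.6 excludes them too.

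**Conclusion.** The point holds as a mismatch between the imputation rule and the regimen, and as a cheap improvement. The documents establish that a Week 3 value from the daily phase can stand in for Week 12, and nothing in them supports equal effects at the two visits. They do not establish the direction of any bias or how many values will be carried.

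Under Case A, the one-sided error for pH is about 3.7% to 10.5% instead of 2.5%. The top of that range requires every planned dropout to have Week 3 as the last value. The chance of a false dose claim is lower than these figures, because all four endpoints must be significant.

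**What to change.** Amend Protocol 7.8.1 and SAP 6.1.2 and 6.3.1 together, before unblinding:

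1. For pH, superficial cells and parabasal cells, make the Week 12 contrast of the MMRM in SAP 6.3.1.6 primary. Name Week 12 explicitly, since the SAP also reports an overall contrast. Move LOCF to sensitivity.
2. For dryness, keep the country-stratified Wilcoxon test and apply it to multiply imputed Week 12 scores.
3. Add one placebo-based (reference-based) sensitivity analysis for all four endpoints. MMRM and standard multiple imputation assume that dropouts behave like women who stayed in their arm.
4. State how Early Termination values are used: when they count as Week 12, and how timing after the last dose matters.
5. Report by arm how many Week 12 values are carried from Week 3 in the LOCF analysis.

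The cost is SAP and protocol wording, a little more programming, and less direct comparability with earlier LOCF results. The MMRM and its gatekeeping table are already planned, and the sample size stays at 70 per group.

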6.1.3 Pooling of Investigative Sites

Sites will be pooled according to country for inclusion as an effect in the statistical models. It is recognized that the pooling of sites in this manner preserves the inclusion of all randomized subjects in the analysis. However, the result of pooling is a loss of the “individuality” of each site being pooled as well as the potential for the pooled site to be associated with an inflated sample size compared to sites that do not require pooling. The effect of this cannot be determined a priori but it is an acceptable approach for the retention of subjects in the analysis.

6.1.4 Determination of Sample Size

A total of 280 female subjects will be enrolled in the study.

The estimates of treatment differences and variability were gained from the results of Study ITFE-2026-C2.

A sample size of 57 in each group will have 90% power to detect a treatment difference for change in severity of vaginal dryness, assuming five categories with proportions in each treatment group as shown in **Table 2** below, using a Wilcoxon rank sum test with a 0.025 one-sided significance level.

Table 2: Assumed Proportions for Wilcoxon Rank Sum Test of Vaginal Dryness

Change in Vaginal Dryness Severity	Proportion in Estriol Vaginal Gel Group	Proportion in Placebo Group
-3	0.189	0.118
-2	0.423	0.196
-1	0.270	0.353
0	0.118	0.333

Change in Vaginal Dryness Severity	Proportion in Estriol Vaginal Gel Group	Proportion in Placebo Group
1	0	0

A sample size of 48 in each group will have 90% power to detect a treatment difference of -0.89 for change in vaginal pH, assuming a common standard deviation of 1.33 using a two-group t-test with a 0.025 one-sided significance level.

A sample size of 24 in each group will have 90% power to detect a treatment difference of 21 for change in proportion of superficial cells, assuming a standard deviation of 26.3 for 0.005% estriol vaginal gel and 14.8 for placebo vaginal gel, using a two-group Satterthwaite t-test with a 0.025 one-sided significance level.

A sample size of 9 in each group will have 90% power to detect a treatment difference of -53 for change in proportion of parabasal cells, assuming a standard deviation of 37.9 for 0.005% estriol vaginal gel and 19.6 for placebo vaginal gel, using a two-group Satterthwaite t-test with a 0.025 one sided significance level.

The largest sample size calculated for a single co-primary endpoint has been considered the sample size required for the whole study, thus, 57 subjects per group are estimated. Accounting for an 18% drop-out rate, and rounding numbers, approximately 70 subjects/group have been finally estimated.

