6.3 Efficacy Analysis

6.3.1 Primary Efficacy Analysis

The four co-primary efficacy variables in this study are:

- Change from Baseline to Week 12 in the severity of vaginal dryness
- Change from Baseline to Week 12 in vaginal pH
- Change from Baseline to Week 12 in the proportion of superficial cells of the vaginal epithelium

- Change from Baseline to Week 12 in the proportion of parabasal cells of the vaginal epithelium

The planned analyses of each of these four endpoints and the gatekeeping procedure to be employed for obtaining conclusions are described in **Sections 6.3.1.1 to 6.3.1.5** below.

The primary analyses will be performed using the ITT population using LOCF methodology, and confirmatory analyses will be performed using the PP population (using observed data only, since having Week 12 data available is a requirement for inclusion in the PP population). It should be noted that, since the statistical tests are one-sided, only one limit of each confidence interval presented (the limit in the direction where Estriol vaginal gel is favorable for each specific endpoint) is of particular interest for analysis. Each statistical test will examine the null hypothesis that Estriol vaginal gel is no different to Placebo against the alternative hypothesis that Estriol vaginal gel is superior to Placebo.

No adjustment for multiplicity will be made, since statistical significance in all 4 co-primary endpoints is required to declare efficacy. The minimal effective dose will be considered to be the lowest dose at which a significant difference is seen (in favor of Estriol) when compared with Placebo.

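### The 57 per group taken as the whole-study size gives 90% power for vaginal dryness alone; for the four-endpoint success rule at 0.005% it gives about 85–88%

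*SAP*

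**What the plan says.** SAP 6.1.4 and Protocol 7.5 contain four separate calculations, each at one-sided 0.025 and 90% power.

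- Dryness: "A sample size of 57 in each group will have 90% power to detect a treatment difference for change in severity of vaginal dryness", using the category proportions in Table 2 and a Wilcoxon rank sum test.
- pH: 48 per group to "detect a treatment difference of -0.89 for change in vaginal pH, assuming a common standard deviation of 1.33".
- Superficial cells: 24 per group, based on "treatment difference of 21 for change in proportion of superficial cells, assuming a standard deviation of 26.3 for 0.005% estriol vaginal gel and 14.8" (the second SD is that of the placebo group).
- Parabasal cells: 9 per group, based on "treatment difference of -53 for change in proportion of parabasal cells, assuming a standard deviation of 37.9 for 0.005% estriol vaginal gel and 19.6" (again, the second SD is that of the placebo group).

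Both sections then conclude: "The largest sample size calculated for a single co-primary endpoint has been considered the sample size required for the whole study". The resulting 57 is raised to about 70 per group for 18% drop-out.

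The success rule is in SAP 6.3.1, which makes no multiplicity adjustment "since statistical significance in all 4 co-primary endpoints is required to declare efficacy". SAP 6.3.1.5 and Protocol 7.8.1.1 apply the same four-endpoint condition at each dose before the next lower dose is tested. Neither document states a joint power or a correlation between endpoints.

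**The concern.** When every one of several endpoints must be significant, the probability of success cannot exceed the power of the weakest endpoint, and it is normally lower. Taking the largest single-endpoint size keeps 90% only if the other endpoints have power close to 1 at that size, or are almost perfectly correlated with the limiting one. The two cell endpoints do have power close to 1 at 57. pH does not, because its own requirement of 48 is not far below 57.

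The size named for the whole study therefore does not carry the 90% from which it was derived. Someone who later reads a failed four-endpoint test at 0.005% against a presumed 90% would understate the role of chance.

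**Working it through.** **Inputs.** All come from SAP 6.1.4 (identical in Protocol 7.5), with one-sided alpha 0.025 and equal groups. The only input from outside the documents is the correlation between endpoints, which is varied.

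**1. Reproducing the plan's figures.**

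- *Dryness.* From Table 2, the probability that an estriol subject improves more than a placebo subject, plus half the probability of a tie, is 0.189×0.882 + 0.423×0.686 + 0.270×0.333 + ½(0.189×0.118 + 0.423×0.196 + 0.270×0.353 + 0.118×0.333) = 0.6667. With the tie-corrected null variance and the exact variance under the alternative, power at 57 is 90.6%; 200,000 simulated trials give 90.4%.
- *pH.* Noncentral t at 48 per group: 90.05%.
- *Superficial cells.* Satterthwaite t at 24 per group: 91.3%.
- *Parabasal cells.* Satterthwaite t at 9 per group: 92.7%.
- *Drop-out.* 57/0.82 = 69.5, rounded up to 70.

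Every stated size is confirmed as giving at least 90% for its own endpoint.

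**2. Each endpoint at 57 per group.**

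- Dryness: 0.9056.
- pH: noncentrality 0.89/(1.33×√(2/57)) = 3.57, power 0.9431.
- Superficial cells: 21/√((26.3² + 14.8²)/57) = 5.25, power 0.9994.
- Parabasal cells: 53/√((37.9² + 19.6²)/57) = 9.38, power above 0.9999.

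**3. Joint power.** Under independence it is the product: 0.9056 × 0.9431 × 0.9994 × 1.0000 = 0.8536. For positive correlation, an equicorrelated multivariate normal was used for the four test statistics.

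| Evaluable per group | Dryness | pH | Joint, independent | Joint, correlation 0.5 | Joint, correlation 0.7 |
|---|---|---|---|---|---|
| 57 | 0.9056 | 0.9431 | 0.8536 | 0.8692 | 0.8797 |
| 62 | 0.9280 | 0.9587 | 0.8895 | 0.9003 | 0.9081 |
| 64 | 0.9355 | 0.9638 | 0.9015 | 0.9107 | 0.9176 |
| 70 | 0.9540 | 0.9757 | 0.9307 | 0.9364 | 0.9412 |

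**4. Limits that do not depend on the correlation.** At 57, joint power cannot exceed the weakest endpoint, 0.9056. It cannot fall below 1 − (0.0944 + 0.0569 + 0.0006) = 0.8481. A correlation of 0.8 gives 0.8865 and 0.9 gives 0.8952, so 90% is reached only close to a correlation of 1. Almost all of the shortfall comes from pH.

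**The case against.** Four points can be made for the plan.

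*No stated number is wrong.* A reader might infer that the plan claims 90% power for the four-endpoint rule and that the claim is false. The documents do not support that: every 90% is tied to one endpoint, and the use of the maximum is openly described. This stands. The defect is an omitted figure together with the description of 57 as sufficient for the whole study.

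*The primary analysis is not limited to 57 per group.* It uses ITT with LOCF on about 70 randomized per group. Dryness, pH and smear are taken at Week 3 and again at early termination (Protocol 6.1.3, 6.1.5), and women who leave after at least one dose are to have that final examination (Protocol 4.2.2). Under independence, 64 contributing women suffice for 90%, which is about 7 of the roughly 13 expected drop-outs per group (70 − 57). This largely stands and is why 93–94% belongs beside 85–88%. It does not remove the point: the plan itself sizes on 57, a woman with no post-baseline value has nothing to carry forward, and values carried forward may show a smaller effect than assumed. The documents do not settle where between the two figures the trial will fall.

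*The correlation is unknown.* True, but the limits in step 4 show that it moves the result at 57 by less than six points.

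*The planned models may be more efficient.* pH will be analysed by ANCOVA with its baseline as covariate. If baseline correlated with change at 0.3–0.5 (an assumption), pH power at 57 would be about 96–98% and joint power under independence about 87–89%. The sizing in the documents takes no credit for this.

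**Conclusion.** The point holds as one of missing and mislabelled power. For 0.005% versus placebo, 57 evaluable per group give about 85–88% for the success rule (correlation 0 to 0.7), against 90% for dryness alone. About 64 give 90% under independence, and about 93–94% is available if all 70 per group contribute as assumed. These figures rest on the plan's effect sizes and SDs, on unadjusted tests as in the plan's own sizing, and on an assumed correlation.

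Two stronger conclusions might be inferred and are not supported. The first is that the trial is underpowered and must enrol more. The enrolled 70 per group may well deliver over 90%, so the documents do not establish a shortfall in the primary analysis. The second is that the loss compounds across the dose sequence, for example to about 69–72% for success at all three doses with 57 per group. That figure assumes the 0.005% effect at every dose, whereas the cell-count SDs are given for 0.005% only and no separate effect is assumed for the lower doses. Nor is success at all three doses the objective. The aim is to identify the lowest effective dose, which can be achieved when a lower dose fails.

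**What to change.** In Protocol 7.5 and SAP 6.1.4, replace the sentence that makes the largest single-endpoint size the requirement for the whole study with a statement to this effect:

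*The 57 evaluable subjects per group are set by vaginal dryness, for which they give 90% power. For significance on all four co-primary endpoints at 0.005% versus placebo, 57 per group give about 85–88% power for assumed correlations between endpoints of 0 to 0.7, rising to about 93–94% if all 70 randomized per group contribute data with the assumed effects. No power is claimed for the 0.002% and 0.0008% doses.*

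The cost is wording in two sections. Enrolment, tests, significance level and decision rule stay as they are. The only downside is that the stated power becomes slightly less favourable.
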